9.2.2. Exclusion Criteria

Patients meeting any of the following criteria will not be included in the study:

1. Enrollment in an interventional clinical trial for A/MBC during the study observation period.

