Real-world outcomes for patients with A/MBC who were treated with palbociclib in combination with AI or fulvestrant have been reported in several publications and at medical congresses. A comparative analysis of palbociclib + letrozole vs. letrozole alone was presented at the European Society for Medical Oncology (ESMO) 2019 congress.⁹ Using the Flatiron Health Analytics Database consisting of U.S. community physicians, a total of 1,416 electronic health records of patients with HR+/HER2- MBC were reviewed to assess the comparative effectiveness of palbociclib + letrozole (n=798) compared to letrozole alone (n=618). Results showed that patients who took palbociclib + letrozole had a median progression-free survival (PFS) of 24.5 months while patients on letrozole alone had a median PFS of 17.1 months (HR=0.68, 95% CI: 0.56-0.84). OS was also favorable for patients taking palbociclib + letrozole compared to patients taking letrozole alone (HR=0.57, 95% CI: 0.41-0.79). Another study reported on the Ibrance Real World Insights

Study (IRIS) involving medical chart review of 652 U.S. patients with A/MBC treated with palbociclib in combination with either AI (n=360) or fulvestrant (n=292).¹⁰ The 12-month progression-free rate was 84.1% for patients treated with palbociclib + AI and 79.8% for those treated with palbociclib + fulvestrant. The 12-month survival rates were 95.1% for palbociclib + AI and 87.9% for palbociclib + fulvestrant.

This present study is designed to examine further real-world evidence on the use of palbociclib, ribociclib, and abemaciclib in both male and female patients with A/MBC. This study is designed to describe patient characteristics, treatment patterns, and clinical effectiveness outcomes in a cohort of patients diagnosed with HR+/HER2- A/MBC who were treated with any CDK4/6i combination therapies with AI in the U.S. community oncology setting.

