16. ECOG/performance status, if available or indication of impaired performance status not otherwise classified as an ECOG rating, at index date (± 60 days). Where available, Karnofsky performance status will be converted to corresponding ECOG score.
17. Comorbidities, indicated as present vs. not indicated as present at index date. The conditions and date of the condition to be assessed will include those assessed as part of the standard Charlson Comorbidity Index. These include myocardial infarction, congestive heart failure, peripheral vascular disease, cerebrovascular accident, hemiplegia, chronic obstructive pulmonary disease, ulcer disease, diabetes, renal disease, connective tissue disease such as rheumatoid arthritis or lupus, Alzheimer's or other dementia, cirrhosis or other serious liver disease, leukemia, lymphoma, metastatic solid tumor (other than breast cancer), and HIV/AIDS.

PFIZER CONFIDENTIAL

18. Other comorbidities of interest, indicated as present vs. not indicated as present at index date: hypertension and hyperlipidemia.
19. Dates of disease progression after index date through the end of the record or the end of the study, whichever occurs first.
20. Documentation of treatment modifications (dose modification, schedule changes, dose delay, hold, or discontinuation) for palbociclib, **CCI** [REDACTED] and reasons for treatment modifications, if applicable, from the index date through the end of the record or the end of the study, whichever occurs first. Date of treatment modification and reason for modification will be collected, if available.
 - Reasons for modification will include: Cost, disease progression, patient refusal/request, toxicity (specify), other (specify), or UD.
21. Oral anti-cancer therapies. This will include all treatments from the index date through the end of the record or the end of the study, whichever occurs first. **CCI** [REDACTED]
22. Documentation of any IV, IM, or subcutaneous anti-cancer therapy not otherwise documented in standard medication tables, including all treatments received from the index date through the end of the record or the end of the study, whichever occurs first. Agent and start and end dates will be collected.

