9.9. Limitations of the Research Methods

This study reflects treatment practice patterns only within the U.S. who are part of the Definitive Oncology Dataset. The majority of the data reflects treatment in community oncology settings (80%). It is possible that treatment patterns may differ in academic centers compared with community settings.

This study is retrospective. With the advent of newer therapies in breast cancer, it is expected that treatment patterns will change during the next few years, and therefore, this study may not be reflective of future breast cancer treatment patterns.

It is possible that patients within the Definitive Oncology Dataset differ from the underlying breast cancer population in ways that may not be measurable; therefore, study results may not be generalizable to other settings.

Some measurements may not be consistently available from patient records in the Definitive Oncology Dataset.

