5. ENDPOINTS AND COVARIATES

- Index date:** Date of A/MBC diagnosis.
- Observation period:** February 3, 2015 through the data cutoff date (end of data curation). Since data curation will start in November 2019, this allows patients to have a potential follow-up of at least 6 months.
- Follow-up:** Patients will be followed from the index date to the data cutoff date, or death, whichever comes first.

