5.3. Efficacy/Effectiveness Endpoint(s)

Variable	Operational definition
Real-world progression-free survival	
Time in months from the initial endocrine-based therapy to the first progression or censoring date will be calculated.
 
For the purpose of this study, lines of therapy will be defined as the following Progression-based lines, in which a disease progression must occur for a new regimen to be interpreted as a new line of therapy.
 
Event: Any death or disease progression. Disease progression is taken to have occurred when a pathology report or radiological scan indicates disease progression and/or there is a physician progress note consistent with that determination. If patients did not die or have disease progression, they were censored at their last visit date during the study period for patients with only one line of therapy.

Overall survival	
Time in months from the initial endocrine-based therapy to death due to any cause or censoring date will be calculated.
 
Event: Any death recorded in the data extract. Patients who did not die will be censored at the time of data cutoff (assuming this is the last date the SSDI is searched).

Real-world tumor response	
Real-world tumor response (rwTR) will be assessed as best overall response for each regimen received within the initial endocrine-based therapy.
 
Responses will be classified as Complete response (CR); Partial response (PR); Stable disease (SD); Progressive disease (PD); Not evaluable (NE); or Undocumented. The date of the first positive response (CR or PR) and of the best overall response for each regimen will be collected.

Response rate	
The number of patients with complete response or partial response divided by the number of patients with at least one tumor assessment while on the initial endocrine-based therapy.

PFIZER CONFIDENTIAL

Time to first positive response	Months from the start date of the initial endocrine based therapy to the date of the first positive response (CR or PR).
Duration of response	Month from the date of the first positive response (CR or PR) to the date of first PD assessment or death. Patients without a PD assessment or death are censored at the the data cutoff date.
Duration of initial endocrine-based treatment	Months from the start date of the initial endocrine-based therapy to the end date of the initial endocrine-based therapy.

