7. STATISTICAL METHODOLOGY AND STATISTICAL ANALYSES

7.1. Statistical Methods

Mean, standard deviation, median, 1st quartile, 3rd quartile, inter-quartile range, minimum, and maximum will be provided when performing descriptive analysis of continuous data. Numbers and percentages will be provided when performing descriptive analysis of categorical data.

An unadjusted Kaplan Meier curve will be drawn to illustrate each time-to-event outcome. Medians and 95% confidence intervals obtained from the Kaplan-Meier curves will be reported.

All data analysis will be executed using statistical software SAS version 9.4 or later.

PFIZER CONFIDENTIAL

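### Trial enrolment at any time up to data cutoff removes a patient from the cohort, so entry to the rwPFS, response and OS analyses depends on events after therapy start, and no visible text limits, counts or discloses this

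*Protocol*

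**What the plan says.** The only exclusion criterion, worded alike in Protocol 9.2.2 and SAP 4.1.2, is "Enrollment in an interventional clinical trial for A/MBC during the study observation period". The protocol does not define the observation period. SAP section 5 does: "February 3, 2015 through the data cutoff date (end of data curation").

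The clock for the effectiveness outcomes starts later. For rwPFS, SAP 5.3 states: "Time in months from the initial endocrine-based therapy to the first progression or censoring date will be calculated". OS and time to first response start at the same point. SAP 4.1 builds the Full Analysis Set from everyone who passes the criteria, so the exclusion carries into every table and figure. SAP 7.1 adds: "Medians and 95% confidence intervals obtained from the Kaplan-Meier curves will be reported".

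Protocol 9.3.2 already has the nurses abstract "Dates of disease progression after index date through the end of the record or the end of the study, whichever occurs first". A trial enrolment date is not among the curated variables. The visible table shells contain no attrition table. Protocol 9.9 says in general terms that "study results may not be generalizable to other settings", without mentioning trial enrolment.

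**The concern.** Eligibility is decided partly by what happens after time zero. Consider two patients who start the same regimen on the same day in routine care and progress at month 14. One goes on to another standard treatment and stays in the cohort. The other joins a trial at month 16 and is removed, along with the month-14 event, the response data and the treatment history. Nothing in the second patient's first-line experience differs.

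Early starters are exposed to this removal for longer than late starters. The planned Kaplan-Meier intervals describe sampling error only and do not reflect the selection. The outcomes affected are those of primary objective 2 (rwPFS, OS, tumour response) and the later-line sequences of objective 1b in SAP Tables 3 and 4. Because the study is descriptive, no test or error rate is at stake. The estimates and their intervals are the study's product, and they are what the selection touches.

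**Working it through.** **1. How long the rule can act after therapy start.** Protocol 9.5 gives ((50/2) + 8) = 33 months of average follow-up. From the dates, 3 Feb 2015 to 1 Apr 2019 is 49.9 months and 1 Apr to 1 Dec 2019 is 8.0 months, so 49.9/2 + 8.0 = 32.95. The figure reproduces. With uniform entry, the rule can act for 8.0 to 57.9 months per patient. Protocol 9.5 gives 1 Dec 2019 as the assumed start of data collection, while the SAP's cutoff is the end of curation, so true exposure is somewhat longer.

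**2. Illustrative rwPFS curves.** Protocol section 7 reports, from two different studies, "patients who took palbociclib + letrozole had a median progression-free survival (PFS) of 24.5 months" and "The 12-month progression-free rate was 84.1% for patients treated with palbociclib + AI".
- Weibull through both figures: shape = ln[ln 2 / (-ln 0.841)] / ln(24.5/12) = 1.943; scale = 24.5 / (ln 2)^(1/1.943) = 29.59.
- Exponential through the median only: S(12) = 2^(-12/24.5) = 0.712, which does not match 84.1%.

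**3. Assumptions that are not in the documents.** A share of observed progressors with more than 1 month of observation left joins a trial and is deleted; 10% of first events are deaths without progression; response, where used, occurs at 2-6 months.

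**4. Result of deleting later joiners** (1,000,000 simulated patients per curve; true median rwPFS 24.5):

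| Progressors joining | Weibull rwPFS | Exponential rwPFS | Weibull DoR (true 20.9) | Exponential DoR (true 24.6) |
|---|---|---|---|---|
| 2% | 24.6 | 24.7 | - | - |
| 5% | 24.7 | 25.1 | 21.1 | 25.2 |
| 10% | 25.0 | 25.8 | 21.4 | 26.0 |
| 20% | 25.5 | 27.5 | 21.9 | 27.7 |

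**5. Against sampling error.** The 95% half-width of the median (1.96 x SD of 2,000 Kaplan-Meier medians) at N = 1100-1300 is 1.1-1.2 months (Weibull) or 2.1-2.3 (exponential). At 5-10% joining, the shifts are 0.2-0.5 and 0.6-1.3 months, inside the half-width. Only the 20% exponential shift (3.0) exceeds it. The shift does not shrink with N. At 1200 retained patients the nominal 95% interval covers 24.5 in 94% (Weibull) or 91% (exponential) of samples at 5% joining, and in 89% or 80% at 10%. The Palbociclib + AI cohort's size is not given; being a subset, its half-width is wider.

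**6. Unequal exposure.** At 10% joining, 7.8% of the earlier-starting half is deleted against 3.3% of the later half (Weibull), or 6.4% against 3.7% (exponential).

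**7. Timing decides the sign.** With 5% of the cohort joining in total, the rwPFS shift is zero when about 50-56% of joiners enrol before progression. If all do, 24.5 reads about 24.2 (Weibull) or 23.6 (exponential).

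**8. OS.** On the exponential curve, with an assumed 20-month median survival after progression, 36-month OS moves from 0.657 to 0.660-0.661 at 5% joining and to 0.662-0.665 at 10%. When enrolment lags progression by 3 months, 12-month OS is flat or slightly lower. The direction is not settled.

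**9. Censoring at enrolment as a repair.** Let 1.2-1.3% of the cohort enrol 0-3 months before they would have progressed and 4.9-5.4% enrol after progression. The current rule reads 25.1 (Weibull) or 26.2 (exponential). Keeping everyone but censoring at enrolment reads 24.7 or 25.0. Keeping everyone and ignoring enrolment reads 24.5 in both.

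**The case against.** A cohort restricted to routine care is a legitimate aim for this study, and trial regimens may be unidentifiable in the chart. Enrolment before therapy start does need exclusion, and enrolment during first-line therapy needs some handling. That part stands. It does not extend to enrolment after an observed progression, which cannot contaminate first-line rwPFS or duration of response.

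The effect is assumed rather than shown, and the larger shifts come from the curve that misses the 12-month figure. This also stands. On the curve that matches both published figures, every shift considered lies within sampling error.

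A reader might infer that the reported rwPFS will be overstated, or overstated materially. The documents do not support that: they give neither rate nor timing of enrolment, and the sign reverses if most joiners enrol before progression. A reader might also infer that censoring at enrolment is the clean remedy. Step 9 shows that it can leave bias when enrolment anticipates progression.

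Nurses verify and document eligibility for each chart (Protocol 9.6), so an exclusion count may be obtainable without redesign. However, no visible shell reports one. Redacted text could bear on this; the statement about reporting covers visible text only.

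**Conclusion.** The structural point holds on the text alone: the exclusion runs to data cutoff, the endpoints start at therapy, the analysis set inherits the rule, and no visible passage restricts, counts or discusses the resulting selection. What the documents do not settle is how much it matters. If joining mostly follows progression, rwPFS and duration of response are biased upward, by about 0.2-0.5 months (Weibull) or 0.6-1.3 months (exponential) in median rwPFS at an assumed 5-10% of progressors joining. If about half or more join before progression, the rwPFS bias vanishes or reverses. The OS direction is unknown. This is worth correcting because the rule removes observed first-line events without benefit to the first-line endpoints. It does not by itself invalidate the study.

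**What to change.** 1. In Protocol 9.2.2 and SAP 4.1.2, limit the exclusion to trial enrolment at or before the start of the initial endocrine-based therapy, or initial CDK4/6i + AI given within a trial. Keep later enrollees for the first-line endpoints.
2. Count progression before enrolment as an rwPFS event. Where enrolment comes first, report rwPFS and duration of response both ignoring enrolment and censoring at enrolment, without presenting the censored version as bias-free.
3. Report OS with and without censoring at enrolment.
4. Label later trial regimens as clinical trial in SAP Tables 3 and 4. Later-line sequences are only partly repaired, since some agents will be unknown.
5. Report the number of trial enrollees by timing: before therapy, on first-line therapy before progression, and after progression.

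Cost: a protocol and SAP edit, one added abstraction item (the enrolment date), and full abstraction of the retained charts. If 1100-1300 is the cohort after exclusion and d the share deleted, the extra charts are N x d/(1-d). At 5% of progressors joining (d about 2.5-2.8%) that is about 29-37. At 10% it is 1100 x 0.051/0.949 = 59 to 1300 x 0.055/0.945 = 76.

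If the sponsor keeps the rule to preserve a routine-care-only cohort, report the count in item 5 for the excluded patients and name the selection in Protocol 9.9.

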9.3. Variables

9.3.1. Regimens and Lines

For purposes of this study, a regimen will be defined as one or more anti-cancer agents given in combination, over a period of time, in which the following conditions hold:

1. All agents start within 60 days of the start of the first agent in the combination, unless the start of an agent later than 60 days after the start of the first agent is specifically indicated as planned at the time of the start of the first agent.
2. No agent is discontinued and replaced by another agent within 60 days of the start of the first agent in the combination.
3. No agent is held and then resumed after an interval of more than 63 days.

Accordingly, unless the record indicates a planned delay in the start of an agent, the addition of a new agent to an existing therapy more than 60 days after start of the regimen constitutes a change of regimen. Holding of an agent for a brief period is not interpreted as a change of regimen. However, the resumption of an agent that is held and then resumed after an interval of more than 63 days is interpreted as signaling a new regimen. Discontinuation of one agent

being used in combination at any point by itself does not signal end of a regimen unless it is the only agent being administered. Occurrence of a disease progression does signal the end of a regimen. After a progression, a treatment being given before the progression will be interpreted as a new regimen—albeit identical to the previous one. This scenario, treatment through progression, occurs in some settings, and is identifiable in study data with the coding rules described here.

For the purpose of this study, lines of therapy will be defined as the following *Progression-based* lines, in which a disease progression must occur for a new regimen to be interpreted as a new line of therapy.

Disease progression is taken to have occurred when a pathology report or radiological scan indicates disease progression and/or there is a physician progress note consistent with that determination. If the radiological scan did not agree with the physician notes, the event will be determined by physician notes.

For the purposes of this study, first line therapy will be defined as the first progression-based line of therapy that contains the first qualifying endocrine-based therapy. The first qualifying endocrine therapy may include palbociclib + AI, or other CDK4/6i combination therapies with AI that the patient receives after diagnosis of A/MBC. Subsequent lines of therapy will be defined in detail in the statistical analysis plan (SAP) as progression-based lines. Regimens within the first progression-based line defined above will be identified.

[figure not shown]

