8. RESEARCH QUESTION AND OBJECTIVES

The objective of this study is to describe the patient characteristics, treatment patterns, and clinical effectiveness outcomes for patients with a diagnosis of HR+/HER2- A/MBC who received CDK4/6i combination therapy with AI as the initial endocrine-based therapy in the A/MBC setting.

Primary Objectives:

1. Among patients with HR+/HER2- A/MBC receiving CDK4/6i combination therapy with AI as initial endocrine-based therapy:
 - a. Describe demographic and clinical characteristics.
 - Demographic characteristics will include age, sex, race, insurance status, menopausal status, and region of residence at A/MBC diagnosis;
 - Clinical characteristics will include stage of initial diagnosis, histology, Eastern Cooperative Oncology Group (ECOG) performance status (where available, Karnofsky performance status will be converted to corresponding ECOG score) and comorbid disease burden, HER2 and Estrogen receptor (ER)/Progesterone receptor (PR) status, number and sites of distant metastasis at A/MBC diagnosis (if applicable); modalities of treatment received prior to A/MBC diagnosis (chemotherapy, hormone therapy, surgery, radiation therapy) and disease free interval (time between completion of adjuvant therapy and diagnosis of A/MBC).
 - b. Describe treatment patterns.
 - Distribution of regimens from the diagnosis of A/MBC through the end of the record;

- Sequence of regimens across lines, through the end of the record of systemic therapy;
- Description of the dosing employed with administration of palbociclib, ribociclib, and abemaciclib. Description of the dosing will include the starting dose, end dose, dose adjustment (dose increase and dose reduction), reasons for dose adjustment (dose modification, schedule changes, dose delay, hold, or discontinuation), discontinuation, reason, and time to dose adjustment (discontinuation).

2. Among patients receiving Palbociclib + AI as initial endocrine-based therapy, examine clinical effectiveness outcomes including:
 - a. Real-world progression-free survival (rwPFS) will be assessed for the first endocrine-based therapy.
 - b. Overall survival (OS) will be assessed from start of the first endocrine-based therapy.
 - c. Real-world tumor response (rwTR) will be assessed as best overall response for each regimen received within the first endocrine-based therapy.

CCI [REDACTED]

[REDACTED]

[REDACTED]

[REDACTED]

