9.2. Setting

9.2.1. Inclusion Criteria

Patients must meet all of the following inclusion criteria to be eligible for inclusion in the study:

1. Female or male sex.

PFIZER CONFIDENTIAL

[REDACTED]

2. Diagnosis (confirmed by clinical review) of A/MBC, defined as breast cancer at stage IIIB, stage IIIC, stage IV or identified as having distant metastasis.
3. Age ≥ 18 years at A/MBC diagnosis.
4. Initiated a CDK4/6i in combination with an AI as initial endocrine-based therapy after A/MBC diagnosis on or after 2/3/2015 and before 4/1/2019.
 - Note that the date of the start of the inclusion period reflects the month that the first CDK4/6i (ie, Palbociclib) received U.S. FDA approval.
5. Evidence of ER or PR positive disease, or absence of any indication of ER and PR negative disease closest to A/MBC diagnosis (ie, patients are eligible without affirmative indication of ER/PR+ status as long as ER/PR- indication is not present).
6. Evidence of HER2 negative disease, or absence of any indication of HER2 positive disease closest to A/MBC diagnosis (ie, patients are eligible without affirmative indication of HER2- status as long as HER2+ indication is not present).

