23. First positive response and best overall response for each regimen from the index date through the end of the first progression-based line of therapy containing the first qualifying endocrine-based therapy, the end of the record or the end of the study, whichever occurs first. Responses will be classified as Complete response (CR); Partial response (PR); Stable disease (SD); Progressive disease (PD); Not evaluable (NE); or Undocumented. The date of the first positive response (CR or PR) and of the best overall response for each regimen will be collected.

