4.2. Subgroups

Summaries of study outcomes may be repeated focusing alternatively on but not limited to the following subgroups of interest—sample size permitting—which will be defined on the basis of:

- Age (years): ≤ 50 , 51-64, 65-74, ≥ 75 ;
- Gender, if number of males is low then we can restrict results to females;
- Race: White, Black, Other;
- Disease stage at initial diagnosis: I or II, III, IV;
- ECOG performance status: 0, 1 or 2, ≥ 3 ;
- Site of metastasis: Visceral, Non-visceral, Bone only;
- Number of metastatic sites: 1, 2, ≥ 3 ;

PFIZER CONFIDENTIAL

- Menopausal status: premenopausal, perimenopausal, Postmenopausal, undocumented;
- Hormone therapy prior to A/MBC diagnosis: yes, no;
- Chemotherapy prior to A/MBC diagnosis: yes, no;
- Surgery prior to A/MBC diagnosis: yes, no;
- Radiation therapy prior to A/MBC diagnosis: yes, no;
- Disease free interval: ≤ 12 months, > 12 months;
- Starting dose: by starting dose levels for Palbociclib, CCI

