5.1. DEMOGRAPHIC AND CLINICAL CHARACTERISTICS

Variable	Operational definition
Demographic characteristics	
Age	Age at A/MBC diagnosis, years
Age category	≤ 50 , 51-64, 65 –74, ≥ 75 years
Sex	Female or Male
Race	White, Black, Asian, Other, Unknown
Region of residence	Based on state where the patient resides: Northeast, Midwest, South, West
Insurance status	Private only, public only, public and private, or neither reported at index date and reported at initiation of the earliest endocrine-based therapy after the index date.
Clinical characteristics	
Menopausal status	(Pre, Peri, Post, UD) nearest in time to the date of, but before, index date.
Type of MBC	De novo MBC (newly diagnosed): Stage 4 at initial BC diagnosis Recurrent MBC: Stages 0-3 at initial BC diagnosis
Modalities of treatment received at any point prior to A/MBC diagnosis	Surgery (yes/no), Radiation (yes/no), Chemotherapy (yes/no), Hormone therapy (yes/no)

PFIZER CONFIDENTIAL

ECOG performance score	ECOG performance at index date (\pm 60 days), 0, 1,2,3,4,5, or missing. Where available, Karnofsky performance status will be converted to the corresponding ECOG score.
Disease stage at initial BC diagnosis	Stage I, II, III, IV, unknown/ undocumented
Disease stage at index date (date of A/MBC diagnosis)	IIIB, IIIC, or IV
Time from initial BC diagnosis to first MBC diagnosis	Months from the date of initial BC diagnosis to the date of metastatic diagnosis.
Disease free interval	The number of months between completion of adjuvant therapy and diagnosis of A/MBC.
Sites of distant metastasis at index date	Bone; Chest Wall; Contralateral Breast; Distant Lymph node(s); Liver; Lung; Peritoneum; Pleural nodules; Malignant pleural effusion; Skin; Brain; Undocumented; Other Specified. All sites will be reported as (yes/no).
Visceral metastasis at index date	Metastasis at one or more of the following sites: liver, pancreas, intestines, lung, heart, malignant pleural effusion, peritoneum, pleura. Other metastasis sites, including bone or non-visceral metastasis, may be present.
Non-visceral metastasis at index date	Metastasis at one or more of the following sites: bone, brain, skin, chest wall, contralateral breast, or distant lymph nodes.
Bone-only metastasis at index date	Bone metastasis, with no metastasis at any other identified site

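### Patients who progressed on A/MBC chemotherapy before the CDK4/6i + AI are numbered as first line, and the visible SAP has no variable, subgroup or table row that shows them

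*Protocol*

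**What the plan says.** **Eligibility.** Protocol 9.2.1, criterion 4 (repeated in SAP 4.1.1) reads "Initiated a CDK4/6i in combination with an AI as initial endocrine-based therapy after A/MBC diagnosis", with a window on the treatment start date. The only exclusion (Protocol 9.2.2, SAP 4.1.2) is "Enrollment in an interventional clinical trial for A/MBC during the study observation period".

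**Lines.** Protocol 9.3.1 uses progression-based lines, "in which a disease progression must occur for a new regimen to be interpreted as a new line of therapy". It then fixes the start of the count: "first line therapy will be defined as the first progression-based line of therapy that contains the first qualifying endocrine-based therapy". It leaves the detailed definition of later lines to the SAP; the visible SAP does not give one.

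**What is to be described.** Objective 1b, in Protocol 8 and again in SAP 2.2, includes "Distribution of regimens from the diagnosis of A/MBC through the end of the record". The index date is the date of A/MBC diagnosis.

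**What the SAP tabulates.** The prior-treatment variable in SAP 5.1 is "Modalities of treatment received at any point prior to A/MBC diagnosis", and the matching subgroup in SAP 4.2 is "Chemotherapy prior to A/MBC diagnosis: yes, no". Both stop at A/MBC diagnosis. Tables 3 and 4 show lines 1 to 3 only. In SAP 5.3, rwPFS, OS and time to first response all start at the initial endocrine-based therapy, and SAP 7.2 uses no covariates.

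**What is collected.** Protocol 9.3.2 and 9.3.3 capture treatments and progressions with dates from the index date. Item 23 of 9.3.2 captures "First positive response and best overall response for each regimen from the index date through the end of the first progression-based line of therapy"; the line meant is the one with the qualifying therapy.

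**The concern.** The cohort is defined by the first endocrine-based therapy, but the line count treats that therapy as the first line of treatment. The two differ for anyone given chemotherapy for A/MBC first. The protocol allows for this: 9.3.4 item 1 derives age at the earliest endocrine-based regimen separately from age at the first treatment regimen after the index date. Stage IIIB and IIIC count as A/MBC, so chemotherapy for stage III disease can also fall in this interval.

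Two things are at stake. Objective 1b is a primary objective, and one class of A/MBC regimen has no place in its tables. The Objective 2 estimates combine patients untreated for A/MBC with patients who have already progressed once, and a reader of the planned tables could not tell how many of the second kind there are.

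**Working it through.** The plan states no figure on this point, so there is none to reproduce. The check follows two types of patient through the definitions; a sensitivity illustration comes after.

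**Patient 1: A/MBC chemotherapy, progression, then palbociclib + AI.**
- Eligible: the palbociclib + AI is the first endocrine-based therapy, and no exclusion applies.
- Under the progression rule in Protocol 9.3.1 the chemotherapy is one line and the palbociclib + AI the next. The first-line definition in the same section then calls the second of these line 1.
- The chemotherapy line comes before line 1. Tables 3 and 4 have no row for it. SAP 5.1 and 4.2 cannot flag it, because it was given after A/MBC diagnosis.
- In Tables 6 to 11 the patient is pooled with everyone else.

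**Patient 2: A/MBC chemotherapy with a response, no progression, then palbociclib + AI.** Let A be the chemotherapy start, R the chemotherapy response, C the palbociclib + AI start and P the progression, with A < R < C < P.
- No progression separates the regimens, so both are in line 1. Table 3 lists regimens within a line, so this chemotherapy is visible.
- Treatment Sequence Duration (SAP 5.2) runs from the first regimen in the line. It starts at A, while rwPFS starts at C. The two cover different intervals for the same line.
- Time to first positive response (SAP 5.3) is measured from C, and nothing requires the response to be dated on or after C. If R is used, the result is R − C, which is negative.
- Duration of response from R is P − R, which exceeds this patient's rwPFS of P − C.
- For response rate, the limit to time on the initial endocrine-based therapy is attached to the denominator. The numerator has no stated date limit.

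**Illustration of pooling, Patient 1 type only.** Inputs: a median of 24.5 months for patients untreated for A/MBC, borrowed from the real-world palbociclib + letrozole study cited in Protocol 7. Assumed, because the documents give neither: a share s of pretreated patients, and either their median m or their hazard ratio HR. With exponential times, solve for the pooled median t:

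(1 − s) × 0.5^(t/24.5) + s × 0.5^(t/m) = 0.5, where m = 24.5/HR.

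| s | HR 1.25 | HR 1.5 | HR 2.0 | m = 15 | m = 12 | m = 9 |
|---|---|---|---|---|---|---|
| 5% | 24.2 | 24.0 | 23.6 | 23.9 | 23.6 | 23.3 |
| 10% | 23.9 | 23.5 | 22.8 | 23.3 | 22.7 | 22.1 |
| 20% | 23.4 | 22.5 | 21.2 | 22.1 | 21.1 | 19.8 |

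Medians of 15 to 9 months correspond to hazard ratios of 24.5/15 = 1.6 to 24.5/9 = 2.7. Across the table the shift from 24.5 runs from about 0.3 months (24.5 − 24.2) to 4.7 months (24.5 − 19.8). The larger figure needs the worst value of both assumptions. In patients, 5% of 1100 is 55 and 20% of 1300 is 260. Those counts are for all eligible patients; the size of the palbociclib + AI subset is not given.

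**The case against.** The strongest reply is that the study asks about first endocrine-based therapy and says so throughout. A reader might infer that the outcomes are reported as first line. They are not: the title, objectives and SAP 5.3 endpoints say initial endocrine-based therapy, the outcome tables are headed by cohort, and Protocol 9.3.1 presents its line definition as specific to this study. That stands. Keeping chemotherapy-pretreated patients in the cohort is a legitimate choice.

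A reader might also infer that the plan ignores treatment between diagnosis and the CDK4/6i. It does not. Objective 1b covers it and the data are collected from the index date. The gap lies in how the SAP carries this through.

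Nor do the documents show chemotherapy responses being credited to palbociclib + AI in Tables 8 and 9. Those tables are by regimen, and item 23 of Protocol 9.3.2 governs collection, not analysis. What remains is the missing date rule, chiefly for Tables 10 and 11.

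It would also be too strong to say that A/MBC diagnosis may date from any time. Protocol 9.5 describes a diagnosis window of 2/3/2015 to 4/1/2019, whereas criterion 4 places those dates on treatment start. The two need reconciling. Either way, chemotherapy can precede the CDK4/6i + AI.

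Finally, the subgroup list in SAP 4.2 is open-ended, and parts of the cohort list and table shells are redacted. Absence can be asserted for the visible text only. An open list still does not supply the missing row in the visible Tables 3 and 4.

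**Conclusion.** The point holds as a mismatch between the protocol and the SAP. When A/MBC chemotherapy ended in progression, the CDK4/6i + AI is numbered line 1 and the earlier line disappears from the visible SAP. Tables 3 and 4 then fall short of Objective 1b, whatever the number of patients. The rwPFS, OS and response tables pool these patients without a count. Chemotherapy without progression stays visible, but it leaves the sequence duration and the response times without a consistent origin.

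The effect on the estimates is not known. The range of about 0.3 to 4.7 months rests wholly on the assumed share, the assumed prognosis and exponential times. The downward direction is argued only for patients who had progressed; for those who responded without progressing the documents support no direction. No shift in OS was calculated. The documents do not show that Objective 2 is biased, only that the reader could not judge whether it is. The sponsor should close the gap before analysis.

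**What to change.** 1. In SAP 5.1 and Tables 2a/2b, add one derived variable: *systemic anti-cancer therapy between A/MBC diagnosis and start of initial endocrine-based therapy: none / given without progression / given with progression*.
2. Relabel line 1 as *first endocrine-based line*, and add a row for earlier A/MBC regimens to Tables 3 and 4.
3. Keep the full cohort as the main analysis. Repeat Tables 6b to 9b as a supportive analysis in patients with *none*.
4. For response rate, time to first response and duration of response, count only responses dated on or after the start of the CDK4/6i + AI regimen.
5. Reconcile the diagnosis-date wording in Protocol 9.5 with criterion 4 in Protocol 9.2.1.

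The analysis changes need no new data, since dated treatments, progressions and responses from the index date are already collected, and the full cohort is unchanged. The cost is SAP wording, one derivation, a few more tables, and a smaller restricted cohort in the repeated ones.
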